The primary study outcome is pain response at 12 months, defined as a 30% improvement in the Brief Pain Inventory (BPI). The main opioid dose outcome is 50% reduction in opioid daily dose. The main composite outcome is the proportion with 30% improvement in pain and 50% decrease in opioid daily dose, representing dual improvements in pain and opioid safety. We will assess secondary patient-relevant outcomes including function, quality of life, symptoms (e.g., depression, anxiety, sleep, fatigue), and adverse effects.

Analytic methods

All participants will be assessed in the arms to which they are assigned. An estimated sample size of 970 patients from 10 sites provides 80% power for a 2-sided chi-squared test comparing pain response rates for TCM and IPT if IPT adds 10% to the response rate, and $> 85\%$ power if IPT adds 11% to the response rate. We will use all follow-up data in repeated-measures logistic regression modeling 30% reduction from baseline in BPI scores. For the second aim, we estimate 80% power power to detect small to moderate effects (Cohen d or standardized difference) in mean BPI scores of 0.35 or more.

We will evaluate heterogeneity of treatment effects in 5 pre-specified subgroups that may be differentially responsive to treatment, at greater risk for opioid harms, or more likely to have difficulty reducing opioids (patients treated with high-dose opioids and those with depression symptoms, post-traumatic stress symptoms, potential substance use disorder (SUD), and fibromyalgia symptoms). We will use repeated-measures linear regression to examine interactions of subgroup with treatment assignment.

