7.3 Statistical Analysis of Primary Aim

We will use all follow-up data in a repeated-measures logistic regression modeling 30% reduction from baseline in BPI scores at the quarterly follow-up assessments. The regression model will use assigned intervention, assessment point, and their interaction as explanatory measures. Assessment points will be incorporated as random effects, with non-zero means and an unstructured covariance, to model potential correlation among outcomes for individuals. Our primary assessment of intervention effects will examine differences in the log odds of attaining a 30% reduction in BPI at the 12-month assessment using a two-sided Wald test (0.05 significance level), together with the corresponding model-based odds ratio point and confidence interval estimates.

To assess the sensitivity of these initial analyses to response bias, we will fit a series of weighted selection model analyses. Each analysis will use an EM algorithm to estimate weights to assign to potential values of the missing outcomes for use in logistic regression. The regression will model the log odds of a reduction in BPI at 12 months using the assigned intervention and relevant baseline measures as predictors. The EM algorithm will jointly use a logistic model for observation of the 12-month outcome to iteratively update the weight estimates. These latter logistic models will be varied to use different combinations of the following variables—12-month outcome, intervention, observation and value of the outcome at prior assessments, and baseline covariates together with pain measurements and services utilization over the follow-up period—as predictors to consider different potential missing at

random and missing not at random mechanisms generating the missing data. The approach outlined above will also be used to examine differences in reduction in opioid use at 12 months, the combination of pain reduction and opioid use reduction, and the BPI severity and interference subscales.

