7.6 Analysis of Tapering Strategies

Among the subset of participants on high-dose opioid therapy at baseline we will modify the analyses discussed above by adding the tapering assignment as an explanatory measure to the

model structure in the same manner as the TCM/IPT measure is included in the models. We will use comparable testing and estimation approaches to assess whether the expanded tapering option results in better outcomes in this subpopulation.

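### Section 7.3 gives each visit of a yes/no outcome its own random effect, so the primary 12-month odds ratio depends on an estimator and a scale that the plan does not name

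*Combined protocol and SAP*

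**What the plan says.** Section 7.3 fits a logistic regression to whether BPI has fallen by 30% at each quarterly visit, with arm, visit and their interaction as predictors. On the within-person structure it says "Assessment points will be incorporated as random effects, with non-zero means and an unstructured covariance", with the purpose "to model potential correlation among outcomes for individuals". The primary assessment is "differences in the log odds of attaining a 30% reduction in BPI at the 12-month assessment using a two-sided Wald test", "together with the corresponding model-based odds ratio point and confidence interval estimates".

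The model is reused. Section 7.3 adds "The approach outlined above will also be used to examine differences in reduction in opioid use at 12 months", and also names the composite. Section 7.6 adds the taper assignment to the "model structure in the same manner as the TCM/IPT measure is included in the models".

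The Abstract says only "We will use all follow-up data in repeated-measures logistic regression modeling 30% reduction from baseline in BPI scores". No section gives a constraint on the random-effect variances, a residual-side or estimating-equation formulation, the scale of the odds ratio (conditional or marginal), an estimation method, or a fallback if the model does not converge. The selection models in 7.3 do use a 12-month-only logistic regression, but as a sensitivity analysis for response bias.

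**The concern.** In a linear model, a random effect per visit is redundant with the residual, but their sum, the total within-person covariance, is identified. The similar wording in 7.4 and 7.5 therefore does no harm. A yes/no outcome has no separate residual scale. Raising a visit's random-effect variance and stretching that visit's means to match leaves almost the same response probabilities. Only the small difference in shape between the logistic and normal curves tells the two apart. The conditional log odds ratio is a difference of those stretched means, so it rises with the variance.

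At stake is the primary estimate and its interval. If the fit fails or wanders, the analyst must choose a constraint, an estimator or a simpler structure after seeing the data, and that choice moves the published odds ratio.

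**Working it through.** **Inputs from the plan.** TCM response 50% and IPT 60% (7.1.1); 776 evaluable of 970 (7.1), so 388 per arm; four follow-up visits; two-sided 0.05.

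**Assumptions, not in the plan.** Random-effect SDs and correlations (ranges shown); interim response of 35/40/45% (TCM) and 40/47/54% (IPT) at 3, 6 and 9 months; complete data for the 776.

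**Step 1: the plan's own figure.** A two-sided chi-squared test with 388 per arm has power 80.1% for 50% versus 60% and 87.1% for 50% versus 61%; 776/0.8 = 970. Section 7.1.1 reproduces.

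**Step 2: the literal model.** logit P(Y_ij = 1 | b_i) = β_arm,j + b_ij, with b_i ~ N(0, Σ) and Σ an unstructured 4×4 matrix. There are 8 means plus 10 covariance elements, or 18 parameters, against 2 × (16 − 1) = 30 free cell probabilities. By count the model is identified, so the question is how strongly.

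**Step 3: odds ratio against the 12-month SD.** For each SD σ, solve p = ∫ expit(β + σz) φ(z) dz for β in each arm. With σ held fixed, SE² = Σ over arms of p(1 − p)/(388 d²), where d = ∫ expit′(β + σz) φ(z) dz.

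Example, σ = 2: β is 0 and 0.668; d is 0.1514 and 0.1464. SE = √[0.25/(388 × 0.1514²) + 0.24/(388 × 0.1464²)] = 0.239, and z = 0.668/0.239 = 2.80.

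| σ | log OR | OR (95% CI, σ fixed) | z |
|---|---|---|---|
| 0 | 0.405 | 1.50 (1.13–1.99) | 2.79 |
| 2 | 0.668 | 1.95 (1.22–3.11) | 2.80 |
| 4 | 1.109 | 3.03 (1.39–6.58) | 2.80 |
| 8 | 2.078 | 7.98 (1.86–34.2) | 2.80 |

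The proportions are the same in every row.

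**Step 4: can the data choose σ?** Take a true SD of 2 and correlation 0.75. Fix the 12-month SD at 1.5, 4, 8 or 16 and refit the rest. The expected deviance rises by at most 0.0018, where 3.84 would exclude a value, while the odds ratio runs 1.77, 3.03, 7.98, 59. Small SDs can be excluded (SD 1 gives a deviance of 7.2); large ones cannot. A second calculation, with other interim rates and correlation 0.9, gave at most 0.03 for SDs from 1.4 to 8.

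**Step 5: full maximum likelihood.** SE of the 12-month conditional log odds ratio from the expected information for all 18 parameters:

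| True SD, correlation | Σ estimated | Σ known |
|---|---|---|
| 2, 0.5 | 12.7 | 0.239 |
| 2, 0.75 | 4.47 | 0.238 |
| 2, 0.9 | 2.43 | 0.238 |
| 1, 0.75 | 5.93 | 0.175 |
| 3, 0.75 | 6.54 | 0.314 |

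At SD 2 and correlation 0.75, z = 0.668/4.47 = 0.15 and nominal Wald power is about 5%. This is a first-order approximation on a very flat likelihood and is indicative only. With no 12-month difference, rescaling the variance moves both arms equally; the SE is then 0.238 whether Σ is known or estimated, so type I error is not inflated.

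**Step 6: penalised quasi-likelihood on the same model.** Small sets of simulated trials gave stable fits and the same answer from different starting values. With a true conditional odds ratio of 1.95, median estimates were 1.57 and 1.70, SE 0.17–0.18, mean z 2.5–2.8. The variances are shrunk, so the estimate lies between the marginal 1.50 and the conditional 1.95.

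**Step 7: an identified alternative.** A single participant random intercept, fitted to data from five settings (SD 1, 2, 3 at correlation 0.75; SD 2 at 0.5 and 0.9) and standardised to the marginal scale, gives an odds ratio of 1.50, SE 0.145 and z 2.8.

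**The case against.** The strongest reply is that the literal reading may not be the intended one. Nearly the same sentence serves the linear models in 7.4 and 7.5, which suggests stock wording for an unstructured within-person covariance. The stated purpose is only to model correlation, and the mention of non-zero means may simply denote the visit effects already in the model. Under a residual-side covariance the odds ratio is marginal and identified. This reading is plausible and cannot be ruled out. But the non-zero-means phrase appears only in 7.3 and is random-effects language, and no passage states the alternative or the scale.

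The second reply is that the instability belongs to full maximum likelihood, which the plan does not name. This also stands. Step 6 shows that quasi-likelihood fits the literal model without trouble and keeps z near 2.5–2.8. A reader might infer from Step 5 that the primary estimate is unusable however it is fitted, or that the trial has 5% power. The documents support neither, because both need an estimator that the plan does not specify. What remains is that one stated model leads to materially different odds ratios, and the stable one is on neither recognised scale.

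Third, a reader might infer that 7.6 carries the problem into Aim 2's main result. It does not: Aim 2's primary outcome is mean BPI (1.1.2), a linear analysis. Only its non-primary yes/no outcomes are touched.

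**Conclusion.** The concern holds in a limited form. Read literally, 7.3 does not determine the primary odds ratio. Under full maximum likelihood the estimate is practically undetermined and the Wald test could lose power. Under penalised quasi-likelihood it is stable at about 1.6–1.7, where the conditional value is 1.95 and the marginal value 1.50. If a marginal covariance was meant, the estimate is sound, but the plan must say so.

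The sizes rest on assumed SDs, correlations and interim response rates. The pattern held across all those tried.

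Type I error, the sample size, the chi-squared power in 7.1.1, the arm-level response proportions and the linear models in 7.4 and 7.5 are not affected. The baseline-adjusted selection models put their odds ratios on a further scale, but they are sensitivity analyses, and that difference alone is not a defect. This should be fixed; it does not invalidate the design.

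**What to change.** In 7.3, for pain response, dose reduction and the composite (and their use in 7.6), replace the visit-level random effects with one of:

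- a marginal repeated-measures logistic model (arm, visit, interaction) with unstructured working or residual-side covariance and robust standard errors, with weighting or imputation for missing outcomes; or
- a single participant random intercept fitted by maximum likelihood, with the 12-month effect standardised to the marginal scale.

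State that the primary odds ratio, interval and test are on the marginal scale. Name the estimator and a non-convergence fallback, for example a 12-month-only logistic regression. Standardising the selection-model results to the same scale is optional. Sections 7.4 and 7.5 can stay.

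The cost is a little analysis work, with no change to sample size or data collection. The first option needs weighting or imputation to be valid under missing at random. The second assumes a simpler correlation structure and needs delta-method or bootstrap intervals.

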7. STATISTICAL ANALYSIS

7.1 Sample Size Considerations

For our power calculations, we used an effective sample of at least 776 patient participants (at least 80% of initial sample size of 970) for the comparison of 12-month outcomes.

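### The missing-at-random sensitivity analyses in Section 7.3 all reduce to the same complete-case fit, so they cannot test different missing-at-random mechanisms

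*Combined protocol and SAP*

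**What the plan says.** The primary analysis in Section 7.3 is longitudinal: "We will use all follow-up data in a repeated-measures logistic regression modeling 30% reduction from baseline in BPI scores at the quarterly follow-up assessments". Earlier responses therefore inform the 12-month contrast.

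The sensitivity analyses are built differently. "Each analysis will use an EM algorithm to estimate weights to assign to potential values of the missing outcomes for use in logistic regression". Two models are involved:

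- **Outcome model.** The "regression will model the log odds of a reduction in BPI at 12 months using the assigned intervention and relevant baseline measures as predictors". No 3-, 6- or 9-month response appears in it.
- **Observation model.** "The EM algorithm will jointly use a logistic model for observation of the 12-month outcome to iteratively update the weight estimates".

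Only the second is changed between versions: "These latter logistic models will be varied to use different combinations of the following variables". The candidate predictors are "12-month outcome, intervention, observation and value of the outcome at prior assessments, and baseline covariates together with pain measurements and services utilization" during follow-up. The stated aim is to cover several missing-at-random (MAR) and missing-not-at-random (MNAR) mechanisms.

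Section 7.3 extends the approach to opioid reduction, the composite and the BPI subscales. Section 7.4 plans similar analyses for the subgroups.

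**The concern.** An observation model can change an EM weight only if it gives different probabilities of being missing to a responder and a non-responder. An MAR version omits the 12-month outcome by definition, so it gives both the same probability. The variables meant to distinguish one MAR mechanism from another therefore have no route to the estimate.

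Two things are at stake:

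- A reader shown several MAR analyses with the same odds ratio would take the agreement as evidence of robustness, when agreement is guaranteed.
- These versions assume more than the primary model does. They need missingness to be random given arm and baseline alone, while the primary model also conditions on earlier responses. If the two disagree, the cause may be bias in the sensitivity analysis itself.

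**Working it through.** **Plan's own figures (context only, not disputed).** For a two-sided 0.05 test with 388 per arm, 50% v 60% gives power 0.801 and 50% v 61% gives 0.871. Allowing 20% loss, 776 / 0.8 = 970. These match Sections 7.1 and 7.1.1.

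**Algebra.** Let p = P(Y=1 | arm, baseline) from the outcome model, and let c(y) = P(unobserved | Y=y, z) from the observation model with other predictors z.

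1. The weight on Y=1 for a missing outcome is w = p·c(1) / [p·c(1) + (1−p)·c(0)].
2. In an MAR version Y is not in the observation model, so c(1) = c(0) = c and w = p·c / [p·c + (1−p)·c] = p, whatever z contains.
3. The outcome-model score is Σ_observed x(y−p) + Σ_missing x(w−p) = 0. At convergence w = p, so the second sum is zero. What remains is the score of the complete-case logistic regression on arm and baseline.

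**Numerical check.** The EM was run as Section 7.3 describes it, on one simulated trial of 970 (assumed data model, 77% observed at month 12).

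| Observation model | Arm log OR | OR |
|---|---|---|
| Complete case, no EM | 0.35353 | 1.424 |
| Intercept only | 0.35353 | 1.424 |
| Arm | 0.35353 | 1.424 |
| Arm + baseline | 0.35353 | 1.424 |
| Arm + baseline + 3/6/9-month responses | 0.35353 | 1.424 |
| As above + arm interactions + utilisation | 0.35353 | 1.424 |
| MNAR: 12-month outcome only | 0.32219 | 1.380 |
| MNAR: outcome + arm + baseline + earlier responses by arm | 0.29052 | 1.337 |

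The largest coefficient difference between any MAR version and complete case was 3e-12. A separate simulated trial gave 0.2812388 for five MAR versions and for complete case. The code does respond when the 12-month outcome enters the observation model, as the last two rows show.

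Standard errors behave the same way. The complete-case value is 0.149. Treating the fractional weights as real data gives 0.131, which is too small, in every MAR version. Section 7.3 names no variance method for the weighted fit.

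**Size of possible bias (assumed mechanism).** Take 50% response at months 9 and 12 in both arms, no true difference and no baseline adjustment. Let r be the correlation between the two binary responses. Latent correlations of 0.5 and 0.7 give r = (2/π)·arcsin(0.5) = 0.33 and (2/π)·arcsin(0.7) = 0.49.

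- At 20% missing, month-9 non-responders miss month 12 at 30% and responders at 10%. Among those observed, the share of month-9 responders is 0.90 / (0.90 + 0.70) = 0.5625. The observed 12-month response is 0.5 + 0.5r(2 × 0.5625 − 1) = 0.5 + 0.0625r.
- With the reverse pattern in the other arm, the false difference is 0.125r, or 4.2 to 6.2 points. With dependence in one arm only it is 0.0625r, or 2.1 to 3.1 points.
- At 5% missing with the same 3:1 ratio (7.5% v 2.5%), the share is 0.975 / 1.900 = 0.5132. The false difference is 0.9 to 1.3 points for opposite directions and 0.4 to 0.6 for one arm only.
- With the same dependence in both arms, the two shifts are equal and the false difference is zero.

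Simulations of the 20% opposite-direction case gave 3.8 to 6.2 points across two implementations. Using the earlier responses by arm reduced this to 0.2 points or less.

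**A true effect under a strong mechanism.** Here missingness depended on the 3-, 6- and 9-month responses in opposite directions by arm, with about 20% missing, over 1,000 trials. Mean log OR was 0.398 with full data (OR 1.49) and 0.128 for the MAR versions (OR 1.14). It was 0.397 (OR 1.49) when the weights came from an outcome model containing the earlier responses and their arm interactions.

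**The case against.** - **The weight formula is inferred.** Section 7.3 prints no E-step and does not say how missing earlier responses are handled. A joint likelihood that also modelled the earlier outcomes would not collapse. This is true, but no such model is described, and the outcome regression is stated to contain arm and baseline measures only. The identity also needs the same baseline measures in every version, which is the plain reading, since only the observation model is varied.
- **The primary model already covers MAR given earlier responses, and the MNAR versions work.** Both points stand. They limit the reach of the problem but do not make the MAR versions informative.
- **An analyst would notice identical results, and Section 7.2 will examine how completeness relates to pain and utilisation.** An analyst probably would notice, but by then the planned check has produced nothing. The descriptive work in Section 7.2 would show a dependence without correcting for it.
- **The bias scenarios are unfavourable.** This stands. No section suggests opposite-direction dropout, 20% is the planning allowance, and Section 7.2 reports completion above 95% in earlier studies. With the same dependence in both arms and true rates of 50% and 60%, the observed difference at 20% missing is still 9.8 to 9.9 points.
- **Imputation from arm, baseline and earlier BPI largely repeats the primary model's assumption.** This is partly right. The gains are follow-up service use and dependence that differs by arm.

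**Conclusion.** The concern holds. Followed as written, every MAR version in Section 7.3 gives the complete-case estimate, so that half of the plan cannot do what it says it will. The result is exact and does not depend on the amount of missing data. It rests on the outcome model and weights as Section 7.3 describes them and on a fixed set of baseline predictors.

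The practical harm depends on the mechanism and the missing rate, both assumed here. Under dependence that differs by arm it runs from about 0.4 to 1.3 points at 5% missing to about 2 to 6 points at 20%, against a design effect of 10 points. The primary test stands, and the MNAR versions do vary. This should be corrected before analysis, but it does not threaten the trial's main result.

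**What to change.** In Section 7.3, replace the MAR versions with one of the following:

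- multiple imputation of the 12-month outcome, done separately by arm, from the 3-, 6- and 9-month BPI values, baseline measures and follow-up service use, followed by the comparison of 12-month response by arm; or
- weighting of observed cases by the inverse of the fitted probability of observation, with the same variables and their arm interactions in the observation model.

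A smaller edit that keeps the EM framework would also work: take the weights from an outcome model that includes the earlier responses by arm, then fit the regression on arm and baseline. Whichever is chosen, state how missing earlier values are handled and how the standard error allows for the missing outcomes. Keep the MNAR versions, and carry the change through to the other outcomes and the Section 7.4 subgroup analyses that use the same approach.

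The cost is SAP wording and standard software. The variables are already named and collected, and the primary analysis does not change.

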7.1.1 Power estimates for primary analyses

Prior research observed 50% of patients achieving a 30% or greater reduction in BPI at one year with a TCM intervention. Assuming a similar response rate for TCM at a significance level of 0.05, a sample size of 970 enrolled participants provides 80% power for a 2-sided chi-squared test comparing pain response rates for TCM and IPT if IPT adds 10% to the response rate, and > 85% power if IPT adds 11% to the response rate. For the second aim examining adding buprenorphine to the tapering protocol, with an unadjusted 0.05 significance level, the estimated proportion of the sample on high-dose therapy (35%) will result in approximately 135 participants per treatment group and provide > 80% power to detect small to moderate effects (Cohen d or standardized difference) in mean BPI scores of 0.35 or more.

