7.2 General Analytic Approach

We will use an intent-to-treat approach, including all patient participants in the arm to which they were originally assigned. Preliminary descriptive analyses will summarize the distributions of the relevant baseline measures for each arm together with outcome distributions across the assessment points. We will summarize completeness of the outcome assessments and examine associations between completeness and the baseline measures as well as pain measurements, receipt of pain medicines outside the VA, and VA service utilization over the follow-up period. In previous and ongoing studies using similar eligibility criteria and follow-up structure, we have observed outcome completion rates in excess of 95% at each assessment time-point and $> 98\%$ of participants have provided outcomes at one or more follow-up time-points. Initial analysis will use all available follow-up data and subsequent sensitivity analyses will examine the potential effect of response bias.

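### The missing-not-at-random sensitivity models in Section 7.3 estimate a coefficient that the data barely inform and do not test arm-differential missingness; a fixed, arm-specific grid with a tipping point would

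*Combined protocol and SAP*

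**What the plan says.** The primary analysis in Section 7.3 is a repeated-measures logistic regression of 30% pain response on arm, assessment point and their interaction, tested at 12 months. Section 7.2 adds that "subsequent sensitivity analyses will examine the potential effect of response bias".

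Section 7.3 then describes those sensitivity analyses:

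- "Each analysis will use an EM algorithm to estimate weights to assign to potential values of the missing outcomes". The weights feed a logistic regression of 12-month response on assigned arm and relevant baseline measures.
- "The EM algorithm will jointly use a logistic model for observation of the 12-month outcome to iteratively update the weight estimates".
- The observation model is varied over combinations of predictors: the 12-month outcome itself, arm, whether prior assessments were observed and their values, baseline covariates, and pain and utilization during follow-up. The stated purpose is to cover both missing-at-random and missing-not-at-random mechanisms.

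The plan thus varies the set of predictors. It gives no fixed value, range or tipping point for the coefficient of the 12-month outcome, and it names no outcome-by-arm term.

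**The concern.** A missing-not-at-random analysis is informative when the analyst sets how far the missing outcomes depart from the observed ones and shows what follows. Here that departure is a parameter to be estimated from data in which the relevant outcomes are absent. The estimate can come only from modelling restrictions, so it may be very imprecise, or may absorb a misfit elsewhere in the model and be read as evidence about dropout.

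The second problem is direction. Under Section 4.3.10 participants and treatment teams know the arm; only outcome assessors are masked. Patients doing badly could plausibly drop out more in one arm than in the other. A single outcome coefficient shared by both arms does not represent that case. It shifts both response rates together and leaves the comparison nearly unchanged, which can look like robustness. At stake is how much weight a significant or null primary result can bear if 12-month loss is substantial.

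**Working it through.** **1. The plan's own figure.** Section 7.1.1 states: "Prior research observed 50% of patients achieving a 30% or greater reduction in BPI at one year with a TCM intervention", and that "a sample size of 970 enrolled participants provides 80% power for a 2-sided chi-squared test" "if IPT adds 10% to the response rate". Section 7.1 bases power on 80% of 970 = 776, or 388 per arm. With pooled variance under the null:

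power = Φ{[|p₁ − p₂|√n − 1.96√(2p̄(1 − p̄))] / √[p₁(1 − p₁) + p₂(1 − p₂)]}

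= Φ{[0.10 × 19.70 − 1.96 × 0.7036] / 0.70} = Φ(0.844) = 0.80.

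For +11 points the result is 0.87. Both stated figures reproduce, so the planning case is 50% v 60% with 20% missing.

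**2. The model as written.** Let Y be 12-month response, R = 1 if observed, A arm, X baseline measures, Z prior outcomes.

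- Outcome: logit P(Y = 1) = β₀ + β₁A + β₂X, giving p.
- Observation: logit P(R = 1) = γ₀ + γ₁A + γ₂X + γ₃Z + δY, giving q₁ when Y = 1 and q₀ when Y = 0.
- EM weight on response for a missing patient: p(1 − q₁) / [p(1 − q₁) + (1 − p)(1 − q₀)].

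If δ is left out, q₁ = q₀ and the weight is p. Read literally, the missing-at-random versions then reduce to complete-case regression on arm and baseline measures, whatever else is in the observation model.

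**3. How well δ is estimated.** Simulated trials of 970 patients, about 20% missing, true δ = 0. Covariate strengths and the correlation with the prior outcome are assumptions; the documents give none.

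| Observation model contains | What identifies δ | 5-95% range of the estimate |
|---|---|---|
| Y, A, and the same covariate as the outcome model | logistic form only | about -14 to +14; 40% of estimates beyond ±2 |
| Y and A; covariate left out (log OR 0.5 per SD) | exclusion of the covariate | about -1.4 to +1.4 |
| Same, log OR 1.0 per SD | exclusion of the covariate | -0.67 to +0.60 |
| Y and a prior outcome that is absent from the outcome regression | a misspecified link | about -13 to -14 in all of 100 trials; a separate run gave below -16 in at least 95% |

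In the last row the outcome regression omits the correlation between prior and 12-month outcomes, so the observation model is forced to account for it through δ. The exact value reflects only where the optimiser stops.

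Leaving arm out of the observation model also identifies δ, by assuming that arm does not affect observation. In a simple version with arm as the only outcome predictor, changing the missing IPT count from 97 by 12 either way moved the estimate from 0 to +1.9 or -2.3.

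**4. What a fixed grid shows.** Within an arm, exp(δ) is the odds ratio of response in observed v missing patients. With k = exp(−δ):

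p_mis = k·o / (1 + k·o), where o = p_obs / (1 − p_obs), and the arm's rate = (1 − m)p_obs + m·p_mis.

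Example, m = 0.20. TCM with k = 4: o = 1, p_mis = 0.80, rate = 0.40 + 0.16 = 0.560. IPT with k = 1/4: o = 1.5, p_mis = 0.375/1.375 = 0.273, rate = 0.48 + 0.0545 = 0.5345. The difference is -2.5 points.

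| k TCM, k IPT | 20% missing: TCM, IPT, difference, OR | 5% missing: difference, OR |
|---|---|---|
| 1, 1 | 50.0%, 60.0%, +10.0, 1.50 | +10.0, 1.50 |
| 4, 4 (shared) | 56.0%, 65.1%, +9.1, 1.47 | +9.8, 1.49 |
| 1/4, 1/4 (shared) | 44.0%, 53.5%, +9.5, 1.46 | +9.9, 1.49 |
| 1/4, 4 | 44.0%, 65.1%, +21.1, 2.38 | +12.8, 1.68 |
| 4, 1/4 | 56.0%, 53.5%, -2.5, 0.90 | +6.9, 1.32 |

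The shared rows barely move the odds ratio; the arm-specific rows do.

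**5. Tipping point.** With 20% missing and an offset on the log odds of response in missing IPT patients only, offsets of 0, -0.5, -1 and -2 give odds ratios 1.50, 1.35, 1.23 and 1.06 (p about 0.002, 0.02, 0.11, 0.67). Significance is lost between -0.5 and -1. With 5% missing, an offset of -3 still gives 1.35 (p about 0.02). These p-values treat filled-in outcomes as observed, so they are somewhat too small.

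**The case against.** A reader might infer more than the documents support, in four ways.

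- **That a listed model has no unique solution.** With arm as the only outcome predictor and arm plus outcome in the observation model, there are 5 parameters against 4 free cell probabilities, and the likelihood is exactly flat in δ. But Section 7.3 puts baseline measures in the outcome regression, so this is not a model it lists. With covariates in the outcome regression and out of the observation model, δ is identified by exclusion, and tolerably well if the covariates predict strongly. The exclusion remains untestable, and the listed combinations include the poorly behaved ones.
- **That these analyses are the only protection against response bias.** They are not. The primary model uses all quarterly outcomes, Section 7.2 examines completeness against baseline and follow-up measures, and Sections 4.3.10, 6.2 and 6.2.2 provide masked assessors, critical measures first, mailed questionnaires and a minimum assessment.
- **That the analyses cannot test the primary result.** Comparing several mechanisms is a limited but real sensitivity analysis.
- **That differential missingness is ignored.** Arm is a named predictor of observation, so different rates of loss are allowed for. What is unnamed is a different dependence on outcome by arm; the text neither states nor excludes it.

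The strongest point against urgency is the expected loss. Section 7.1 uses 80% as a floor for power, and Section 7.2 reports completion above 95% in similar studies. At 5% missing, the 10-point difference keeps its sign even under assumption-free bounds (+4.5 to +14.5 points); at 20% those bounds are -12 to +28. This stands, and it limits the importance of the point.

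**Conclusion.** The point holds in a limited form. The missing-not-at-random models estimate the dependence of observation on the unseen outcome, and that estimate rests on untestable restrictions. It is very unstable when the same covariates enter both models and can be extreme and spurious when prior outcomes enter only the observation model. The named terms do not include the arm-specific departure that could change the conclusion.

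The size depends on loss: -2.5 to +21 points over the grid at 20% missing, +6.9 to +12.8 points at 5%. These figures assume 50% v 60% among those observed, equal loss in both arms, and odds ratios of 1/4 to 4, a range chosen for illustration. The primary test is unaffected. This is a cheap improvement, worth making in case loss approaches the planning figure.

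**What to change.** Keep the EM-weighting framework. In Section 7.3, replace estimation of the 12-month outcome coefficient with a fixed offset in the observation model, set separately by arm on a pre-specified grid (for example odds ratios 1/4, 1/2, 1, 2 and 4). Report the arm effect and its confidence interval over the grid, and state the tipping point at which the conclusion changes. If prior-assessment outcomes enter the observation model, put them in the model that generates the EM weights for the missing outcomes as well.

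The cost is SAP wording and 5 × 5 = 25 fits with the same code. The downside is a table of results in place of one estimate. Section 7.3 extends the approach to the other main outcomes and Section 7.4 uses similar analyses for subgroups, so the same wording would serve there.
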